## Conflict of Interest: None.

#### Inclusion criteria:

- Patient provides informed consent.
- Patient is over 21 years of age.
- Patient has had a significant disabling, medication-refractory upper extremity tremor with no evidence of non-ET central nervous system disease or injury for at least three (3) months prior to implantation of Activa SC PC, or RC device.
- Patient receives Vim electrode and Activa SC, PC, or RC device implants, and recovers fully after surgery.
- Patient is available for study participation after their clinical programming appointments for six months.

## **Exclusion Criteria:**

- Medication related movement disorders.
- Any suspicion of Parkinsonian tremor, including presence of Parkinsonian features such as bradykinesia, rigidity, or postural instability.
- Severe medical co-morbidity including cardiovascular disorder, lung disorder, kidney disease, continuous neurological disease, hematological disease, or frailty that impact tolerability of the surgery as judged by the screening physicians.
- Patient is undergoing a lead revision surgery.

**Timeline:** Figure 3 depicts the proposal timeline of the project until the study ends. Currently, there are 13/20 patients recruited for the closed-loop study. We will finish recruiting for this study in December 2020 with the last subject visit in June 2021. Between now and project end (July 2021), we will recruit 10 ET-DBS patients for a one-day speech assessment. This is highly feasible since 2-8 ET-DBS patients are seen in clinic weekly. Throughout the closed-loop study, these patients will also undergo the same speech testing.

Figure 3. Proposed timeline until project ends

**Data Safety Monitoring Board (DSMB):** This study will have a designated DSMB composed of three members (A neurologist, a non-clinician scientist, and a non-neurological physician) without ties to the current study or any conflicts of interest. The DSMB will be charged with the duty of meeting every 6 months to discuss all of the AE's for the study. The safety experience will be frequently reviewed by the Data Safety Monitoring Board (DSMB). The DSMB will be informed of all serious adverse events and all mild adverse events which are potentially device related in the opinion of the investigator. The DSMB will designate each AE as mild or severe; as device related, uncertain to be device related or not device related; and as anticipated or unanticipated. Once the first subject is enrolled, the DSMB will meet by teleconference every 6 months until all subjects have completed the 6-month postoperative primary outcome assessment. The DSMB has the authority to suspend further enrollment pending investigation of safety concerns raised by SAEs occurring in the trial. The DSMB has a stopping rule for more than one death or more than 1 suicide deemed to be device related.

Adverse Event Reporting: Once a subject is enrolled into the study, continuous close monitoring will be conducted by the Principal Investigator (PI) in conjunction with the Co-PI and other investigators as well as the University of Florida's Institutional Review Board (IRB), through annual reports of progress and by immediate notification of serious and unanticipated adverse events by the PI to the IRB.

Stopping rules for the study have been established: This study will be suspended by the DSMB only if an unexpected and severe neurological complication occurs and they deem suspending or stopping the study appropriate. Specific examples that would warrant suspending the study include the following, only in the event that they do not reverse with adjustment or discontinuation of the therapy:

- worsening of symptoms
- neurological events such as changes in memory, cognition, and motoric or sensory modalities (the exception to this would be persistent dysarthria, which has been reported with PD and may be an acceptable side effect if symptoms are diminished.

**Statistical Analysis:** All statistical analyses will be performed in R 3.5.2. TRS scores and hand acceleration measures across different stimulation conditions (off, cDBS, rDBS) were assessed using a mixed model ANOVA with the participant as a random effect. All post-hoc comparisons were Bonferroni corrected. Equivalence testing was performed using two one-sided tests. Epsilon, or the region of similarity, for total TRS, contralateral TRS, or hand acceleration were 2 points, 1 point, and 0.1 m/s, respectively.

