**Sample size:** This will be a pilot study designed to assess the feasibility, safety and potential effectiveness of novel stimulation patterns. We will enroll 20 ET patients with kinetic or intention tremor scheduled for DBS implants (Activa SC, PC or RC) in the Vim over the course of 3 years. The study was designed to utilize each patient as their own control, and to compare results against the performance of motor symptoms versus open-loop DBS. UF has implanted 27 ET patients with Activa SC in 2014 alone. The feasibility of recruiting 20 subjects in 3 years therefore is very high. These patients will all receive these implants as standard of care and the only difference will be the trial of responsive DBS. Additionally, we will enroll 10 DBS patients with ET in- clinic along with the 20 closed-loop patients to quantify the effects of different stimulation paradigms on speech, namely open-loop, closed-loop, no stimulation, and intermittent stimulation. There are on average 2-8 ET-DBS patients in clinic every week. Therefore, the feasibility of recruiting 10 patients for a one-day study is high.

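### Single-step Bonferroni on the three pairwise comparisons costs power for rDBS versus cDBS that Holm would recover at the same within-outcome family-wise error

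*Combined protocol and SAP*

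**What the plan says.** The Statistical Analysis section of the combined protocol and SAP takes as its data "TRS scores and hand acceleration measures across different stimulation conditions (off, cDBS, rDBS", in brackets, and says that these "were assessed using a mixed model ANOVA with the participant as a random effect". On multiplicity it has one sentence: "All post-hoc comparisons were Bonferroni corrected". It gives no alpha, no sidedness, no definition of the family and no step-down or gated rule.

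It then adds a separate inference: "Equivalence testing was performed using two one-sided tests". The margins are given as "Epsilon, or the region of similarity, for total TRS, contralateral TRS, or hand acceleration were 2 points, 1 point, and 0.1 m/s"² (the exponent belongs to the unit). The section does not name the two conditions that this test compares, or say whether it is adjusted.

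The design is within-subject: "The study was designed to utilize each patient as their own control" (Sample size). The planned number is 20, and the Timeline section reports "Currently, there are 13/20 patients recruited for the closed-loop study". The Research Plan describes the study as exploratory and not powered as a clinical trial.

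**The concern.** Three conditions give three pairs per outcome. Two of them set off-stimulation against an active mode and will probably show large effects, because entry requires disabling, medication-refractory tremor and settings are optimised for each patient. The third, rDBS against cDBS, is the comparison that the study exists to make (Summary of Methodology).

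Single-step Bonferroni gives each pair one third of alpha and never reuses what the off contrasts no longer need. A step-down rule does reuse it. In a sample of at most 20, the avoidable loss of power falls on the central contrast, and the results are meant to inform a larger trial.

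**Working it through.** The documents give no alpha, power, effect size or SD, so there is no figure of theirs to reproduce.

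**Inputs from the documents:** three conditions; three outcomes with margins (total TRS, contralateral TRS, hand acceleration); n = 20 planned, 13 recruited so far; each patient as own control.

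**Assumptions:** alpha 0.05 two-sided; family of three pairs within one outcome; one paired difference per patient; standardised paired difference dz (mean difference divided by its SD) from 0.5 to 0.8.

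**1. Thresholds.** Bonferroni: 0.05/3 = 0.0167 for every pair. If the family instead pooled three outcomes, it would be 0.05/9 = 0.0056. Holm orders the p-values and tests them at 0.05/3, 0.05/2 and 0.05, stopping at the first failure. If both off contrasts are rejected first, rDBS versus cDBS is tested at 0.05.

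**2. Why error control is kept.** Holm rejects everything that Bonferroni rejects, under the same family-wise guarantee. With three means, if one pairwise equality is false, at most one other can be true. Shaffer's rule uses this to test both remaining pairs at 0.05 after the first rejection.

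**3. Power.** Paired t-test, df = n − 1, noncentrality dz × √n. Two-sided critical values at 0.0167 and 0.05 are 2.625 and 2.093 for df 19, and 2.779 and 2.179 for df 12. For example, dz 0.6 at n = 20 has noncentrality 0.6 × 4.472 = 2.683.

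| dz | n = 20: at 0.0167 | n = 20: at 0.05 | n = 13: at 0.0167 | n = 13: at 0.05 |
|---|---|---|---|---|
| 0.5 | 37.3% | 56.5% | 21.2% | 38.2% |
| 0.6 | 53.5% | 72.1% | 31.4% | 51.2% |
| 0.7 | 69.1% | 84.4% | 43.3% | 64.0% |
| 0.8 | 81.8% | 92.4% | 55.8% | 75.4% |

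**4. Dependence on the off effect.** The 0.05 columns assume that both off contrasts are rejected. Holm itself was simulated at n = 20 with 40,000 trials, assumed condition SDs of 8 (off), 4 and 4, and dz 0.6. With an off shift of 12, power is about 54% with Bonferroni and 72% with Holm. With shifts of 8 and 6, Holm gives about 65% and 60% against about 53% with Bonferroni. The gain shrinks but does not become a loss.

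**5. Family-wise error under Holm.** Simulated at about 4.9% when only off differs and 4.3–4.7% under the global null.

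**6. What is given up.** When only off differs, the false-positive rate of rDBS versus cDBS is about 1.7% with Bonferroni and 5% with Holm. If rDBS equals cDBS on all three outcomes, the chance of at least one false difference is at most 3 × 0.0167 = 5% with Bonferroni. Under Holm it is at most 3 × 0.05 = 15%, or 1 − 0.95³ = 14.3% if the outcomes were independent, and less if they are positively correlated.

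**7. The equivalence test.** Take a true 2-point loss on total TRS and an assumed SD of the difference of 3.0 (dz 0.67). At n = 20 the difference test detects it in 64% of trials at 0.0167 and 81% at 0.05. The equivalence test with the 2-point margin, at an assumed 0.05 per side, wrongly declares equivalence in about 5%, whichever post-hoc correction is used.

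**8. Pair-specific errors.** If off is much more variable (assumed SD 6 against 2.12), Holm with the pooled ANOVA error detects the 2-point loss in 27% of trials, against 81% with pair-specific errors. Under the global null, the pooled-error version also has a family-wise error of 5.7%, against 4.0%.

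**The case against.** Bonferroni is valid and conventional, the study is an unpowered pilot, and no decision is tied to this p-value. That stands, and it limits the point to an inexpensive improvement.

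A reader might infer that the stricter threshold works in an unsafe direction, making it easier to find no significant difference and so to call closed-loop as good as open-loop. The documents do not support this. Nowhere do they say that a non-significant difference will be read as similarity. The same section gives that question to two one-sided tests, and step 7 shows that their false-equivalence rate does not depend on the post-hoc correction. Nor is the difference test the only place where a loss could appear, since the interval behind the equivalence test could lie beyond the margin.

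A reader might also infer that Bonferroni buys nothing. That is true only against a 5% target within one outcome. It does hold this contrast to about 1.7%, with incidental protection across outcomes (step 6). The plan does not claim that protection, but Holm within each outcome would give it up.

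The 0.0167, the effect sizes, the SDs and the off effect are all assumptions. The paired t-test only approximates the planned mixed model, and responsive stimulation is delivered over visits 3–6, so a single difference per patient may not be the unit of analysis.

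**Conclusion.** The point holds as one of efficiency. Against a 5% family-wise target within each outcome, single-step Bonferroni is dominated by Holm or Shaffer. For rDBS versus cDBS at n = 20, the avoidable loss is about 15 to 19 percentage points of power at dz 0.5 to 0.7. This requires a two-sided alpha of 0.05, a family of three pairs per outcome, and rejection of both off contrasts. Those rejections are likely, but the documents do not show them. With a weaker off effect the gain falls to about 7 points (53% to 60% in the simulated case). The consequence is limited to the difference test. Importance is low, and the change is close to free.

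**What to change.** In the Statistical Analysis section, replace the Bonferroni wording with Holm step-down adjustment of the three pairwise comparisons within each outcome, using pair-specific rather than pooled errors. Shaffer's rule would also serve. State alpha, its sidedness and the family. Say which two conditions the equivalence test compares and whether it is adjusted. Report the unadjusted 95% interval for rDBS minus cDBS for each outcome, so that the size of any loss is visible whatever the p-value.

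The cost is a few words in the SAP and small changes to the R code, with no new data. The downside to acknowledge in the text is the rise in the false-positive rate of this one contrast from about 1.7% to 5% per outcome, and the loss of incidental protection across the three outcomes. If control across outcomes is wanted, the family definition should say so.

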# WEARABLE SENSOR DRIVEN CLOSED-LOOP DEEP BRAIN STIMULATION

#### NCT03051178

#### **Investigators:** [name], University of Florida, Biomedical Engineering [name], University of Florida, Neurology

Background: The clinical value of a smarter deep brain stimulation (DBS) system that responsively stimulates when pathologic symptoms are present, or adaptively modifies stimulation parameters to match the degree of pathology has been long recognized within the neuromodulation community[1]. Continuous, or open-loop DBS may not be necessary for disorders that are paroxysmal. Hence, intermittent DBS delivered only when pathological activity is present might be equally effective and decrease adverse events. Compared to intermittent stimulation on demand, continuous DBS results in unnecessary disruption of normal brain function and has been linked to serious side effects including dysarthric speech and dysphasia[2], [3]. Open-loop DBS also results in rapid battery depletion necessitating frequent surgery for pulse generator replacements. Hence, closed-loop DBS has been hypothesized to have the following potential advantages compared to open-loop DBS: i) the provision of a better and tailored approach for individual patients, ii) the ability to address the paroxysmal symptoms, iii) reduced adverse side effects, and iv) prolonged battery life (fewer number of battery replacement surgeries). The proof-of-concept of these hypotheses, however, has been lacking and the clinical efficacy of closed-loop DBS remains to be demonstrated in movement disorders.

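### Equivalence of rDBS and cDBS is tested on condition means with participant as the only stated random effect, so it can pass while a minority of patients do worse, and pooled visits can give too small a standard error

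*Combined protocol and SAP*

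**What the plan says.** The whole analysis is one paragraph, Statistical Analysis. TRS scores and hand acceleration under off, cDBS and rDBS "were assessed using a mixed model ANOVA with the participant as a random effect". It continues: "All post-hoc comparisons were Bonferroni corrected". On equivalence it says: "Equivalence testing was performed using two one-sided tests". The margins follow: "Epsilon, or the region of similarity, for total TRS, contralateral TRS, or hand acceleration were 2 points, 1 point", with 0.1 m/s² for hand acceleration.

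The paragraph does not state the level of the one-sided tests, the pair of conditions compared, which visits enter, or how repeated visits are handled. It has no participant-by-condition term and no per-patient summary, and no other section supplies one.

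Other sections bear on the point:

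- Background lists, among the hoped-for advantages of closed-loop DBS, "i) the provision of a better and tailored approach for individual patients".
- Sample size: "This will be a pilot study designed to assess the feasibility, safety and potential effectiveness of novel stimulation patterns". It also says "We will enroll 20 ET patients with kinetic or intention tremor scheduled for DBS implants", each serving as their own control.
- Research Plan sets stimulation parameters for each subject. Recordings from visits 1 and 2 supply the control feature, and responsive stimulation runs at visits 3 to 6. Detector weights are tuned to a sensitivity for which no number is given. The study is described as exploratory and unpowered, with its results to inform a larger trial.

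**The concern.** Each patient's rDBS result depends on individually set stimulation and on a detector that seems to be fitted to that patient's own recordings. The rDBS-minus-cDBS difference may therefore vary from patient to patient. One plausible pattern is little change in most patients and a clear loss in a few. A test on the mean dilutes that pattern, and nothing else in the plan would show it.

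There is a second, technical effect. If visits 3 to 6 are pooled with a participant intercept only, the repeated differences within a patient are treated as independent information about the average effect. When the true effect varies between patients they are not independent, and the precision of the mean difference can be overstated.

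At stake is an equivalence statement that a reader takes to cover patients generally, and a larger trial planned on it.

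**Working it through.** The plan gives no power, SD or sample-size calculation, so there is no figure of its own to reproduce.

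**Inputs.** From the documents: n = 20 and epsilon = 2 points for total TRS. Assumed: the pair is rDBS against cDBS, tested on the mean; 5% per side, with 2.5% and 5%/3 as alternatives (the last in case the Bonferroni rule extends to TOST); noise SD of the per-patient difference 1 to 5 points. The scenario of 4 patients losing 4 points each and 16 losing nothing is constructed for illustration.

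**Step 1: no noise.**

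- Mean = 4 × 4 / 20 = 0.80.
- SD = sqrt[(4 × 3.2² + 16 × 0.8²) / 19] = sqrt(51.2 / 19) = 1.64. SE = 1.64 / sqrt(20) = 0.367.
- 90% CI = 0.80 ± 1.729 × 0.367 = 0.17 to 1.43, inside ±2, so equivalence is declared.

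**Step 2: how much noise stops it.** Set 0.80 + 1.729 × sqrt[(2.695 + s²) / 20] = 2. Then sqrt(2.695 + s²) = 1.2 × 4.472 / 1.729 = 3.10, so s = 2.63 points. At 2.5% per side (t = 2.093) s = 1.97.

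**Step 3: probability of declaring equivalence** (paired TOST, 100,000 simulated trials per cell).

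| Noise SD | 4 of 20 lose 4; 5% | 4 of 20 lose 4; 2.5% | 4 of 20 lose 4; 5%/3 | Nobody loses; 5% |
|---|---|---|---|---|
| 1 | 97% | 89% | 81% | 100% |
| 2 | 67% | 50% | 41% | 99% |
| 3 | 42% | 25.5% | 18% | 78% |
| 4 | 21% | 8% | 4% | 39% |
| 5 | 7% | 1% | 0.5% | 12% |

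Timeline reports "Currently, there are 13/20 patients recruited for the closed-loop study". If only 13 were analysed and 3 lost 4 points, the 5% column would read 61%, 36%, 18%, 6% and 1.5%.

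A model on one off, cDBS and rDBS score per patient, with a pooled residual, gives 74%, 59%, 26% and 4% at noise SD 2 when the off-state response varies between patients with SD 0, 2, 4 and 6.

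**Step 4: standard error when visits are pooled.** Take cDBS and rDBS at V = 4 visits, with residual variance σ² per score and between-patient SD τ of the true difference.

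- Correct SE² = (τ² + 2σ²/V) / n.
- With a participant intercept only, residual df = 160 − 20 − 1 = 139, expected residual mean square = σ² + (V/2)(n − 1)τ² / 139 = σ² + 0.273τ², and SE² = 2 × mean square / (nV).
- Let σ² = 2, so that a single-visit difference has noise SD 2. For τ = 2 the mean square is 3.09. The model SE is sqrt(6.19 / 80) = 0.278 and the correct SE is sqrt(5 / 20) = 0.500.
- If the true mean difference sits exactly at the margin, the chance of declaring equivalence is about Φ(−1.656 × 0.278 / 0.500) = 18%, against a nominal 5%. The same formula gives 11% at τ = 1 and 24% at τ = 4.

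Simulation over residual SDs of 1 to 3 points and τ of 1 to 4 gives roughly 7% to 25%. Testing each patient's mean difference instead keeps it at about 5%.

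This error can reverse. If the off condition is pooled in and varies strongly between patients, it inflates the shared residual. With off-state SD 4 and σ² = 2, simulated false equivalence is 2.5%, 9.5% and 20% at τ = 1, 2 and 4. If only one cDBS and one rDBS score per patient were analysed, the interaction would sit in the residual and this step would not apply.

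**The case against.** Testing equivalence of means is the ordinary use of TOST. The plan claims nothing about individuals, calls itself exploratory, and ties no go/no-go rule to the result. All of that stands, and it limits the point to analysis and reporting.

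Four stronger readings are tempting, and the documents support none of them.

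- **That the wider SD never stops TOST from passing.** It can. In the scenario above, TOST fails more often than it passes once noise is somewhat above 2.6 points at 5% per side, and the documents give no SD.
- **That far larger losses would still pass**, such as 2 patients losing 9.1 points or 4 losing 5.5. Those limits need exactly zero difference in everyone else. With noise SD 1 they pass in only about 41% and 42% of trials.
- **That a detector failing in a few patients is the established likely outcome.** Patient-by-patient training is inferred from Research Plan; only stimulation parameters are explicitly individual. Tuning for sensitivity and optimising the stimulation settings both work against missed events.
- **That a loss beyond epsilon, or twice epsilon, means that patient has lost tremor control.** Epsilon is a margin for comparing conditions, and no individual threshold is stated.

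A bare count of patients beyond epsilon can also mislead. With noise SD 2 and no true change, 1 − Φ(1) = 15.9% of patients, or 3.2 of 20, exceed 2 points by chance. Averaging four independent visits lowers this to 1 − Φ(2) = 2.3%, or about 0.5 of 20.

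**Conclusion.** The point holds in a conditional form. The plan's equivalence test concerns the average only, and a minority who do worse need not stop it from passing. For 4 of 20 patients losing 4 points, the chance of passing runs from 97% down to 7% as noise SD goes from 1 to 5 points at 5% per side. It is lower at stricter levels. Where noise is low enough for TOST to succeed reliably when nobody loses (SD 1 to 2), it also passes this pattern in at least two thirds of trials at 5% per side.

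If visits are pooled under a participant intercept alone, false equivalence at the margin may rise from 5% to roughly 7% to 25% in the two-condition case. Variation in the off condition may offset or reverse that.

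These sizes rest on assumed SDs, an assumed level and an assumed comparison. The gap itself, with no participant-by-condition term and no per-patient output, is plain from the text. It deserves correction because the study asks about feasibility and tailoring to the individual, and its results are meant to inform a larger trial.

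**What to change.** In Statistical Analysis:

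1. State that the equivalence comparison is rDBS minus cDBS, give the level per side, and say which visits enter.
2. Add a participant-by-condition random effect. Alternatively, run the TOST on each patient's mean rDBS-minus-cDBS difference over the visits where both were recorded. For a patient who consents again for the second side, keep the sides separate but clustered within the patient, so that one side cannot mask the other.
3. Report the between-patient SD of the difference, and list or plot every patient's difference for each endpoint.
4. Word a passing TOST as equivalence on average.
5. Optionally, report how many patients worsened by more than a prespecified amount, with an exact 95% CI (for example 4/20 = 20%, 5.7% to 43.7%). Label it descriptive, and say that epsilon is a group margin and that rating noise alone puts some patients over it.

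The cost is a few lines of text and no new data, since each patient is already their own control and rDBS runs at visits 3 to 6. The downside is that the equivalence interval may become wider, so equivalence may be harder to show.
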